7.10. ADDITIONAL SENSITIVITY ANALYSES

7.10.1. Item-level Missing Data

For MDS-NMS and MDS-UPDRS Parts I, II, and III, missing item-level scores may be imputed under certain circumstances. For MDS-NMS, a missing item-level score may be imputed with the average of the non-missing items for a given domain provided that there is no more than 40% missingness within that domain. This means that missing items from a 2-question domain may not be imputed. If all items in a domain are not scored after the item level imputation, that domain score is considered as missing, and the corresponding total score will be missing.

For MDS-UPDRS Part I, a single item-level missing value can be imputed with the average of the non-missing values for that Part if no more than 1 missing values exists. For MDS-UPDRS Part II, item-level missing values can be imputed with the average of the non-missing values for that Part if no more than 2 missing values exist. For MDS-UPDRS Part III (in-clinic assessment), item-level missing values can be imputed with the average of the non-missing values for that Part if no more than 7 missing values(Goetz, Luo et al. 2015).

For MDS-UPDRS Part III captured virtually and MDS-UPDRS Part IV, no item level missing values will be imputed.

7.10.2. Missing data

The study protocol has been designed with the objective of minimizing missing data as much as possible. The Study Device has been designated as a Non-Significant Risk Device by the US FDA. Furthermore, the same treatment waveforms that will be used in this study were found to be highly tolerable in previous studies in PD (Wilkinson, Podlewska et al. 2016, Wilkinson, Podlewska et al. 2019, Wilkinson, Podlewska et al. 2019) and episodic migraine (Wilkinson, Ade et al. 2017). Therefore, it is anticipated that any data missing in this trial will be at random and not a result of the treatment arm. Analysis will be conducted using MMRM to allow for unbiased estimation of treatment effect in the presence of missingness at random. (Yuan 2014)For the full MDS-UPDRS Part III collected at the baseline visit 2 (day 29) and end of treatment visit (113) and not collected during baseline 1 (day 0) and interim visits at days 57 and 85, missing item-level values will be imputed using the method described in the previous section. If a missing Day 113 assessment exists after the item level imputation, then the last available post-baseline virtual assessment (Day 57 or Day 85) will be imputed after the value has been prorated using the formula: prorated value = virtual value*(132/108). If this value is utilized the suitably prorated value for Baseline 1 (Day 0) will be utilized rather than the Baseline 2 (Day 29) value.(Rashid 2021) These imputed values for missing data would be applied to both the composite measure for MDS-UPDRS I, II & III and the MDS-UPDRS III secondary outcome measures.

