Randomization will occur only after all scheduled assessments and activities have been completed and normal findings on the ear exam is verified and will occur by selecting an envelope from the randomization package, scanning the bar code to the Device and ensuring that the treatments are loaded. The participant and study partner will be trained on how to use and care for the Device, take it home and commence with twice daily treatments.

Clinician version – not for patient use

Treatment Period: The 12 weeks (84 days +/- 3 days) following the pre-treatment baseline period constitute the treatment period. Participants will self-administer treatments twice daily for the full treatment period up until the scheduled end of treatment visit. Treatment adherence will be recorded by the device.

Study staff will confirm and document that they remain blinded to treatment allocation at the beginning of every study visit after randomization. If a study staff member directly responsible for assessment or safety evaluation becomes unblinded, they will no longer be eligible to complete the delegated study assessments per the protocol for that participant.

Phone contacts: (days 43, 56, 71, 84, 99, 112: +/- 1 day)

Participants will complete interim assessments at weeks 8 (day 56) and 12 (day 84). During phone calls scheduled every 2 weeks, study staff will review concomitant medications, potential adverse events and device treatment adherence and issues with the study participant. Study sites are encouraged to have continuous communication with the study participant and study partner outside of the defined protocol visits, in the manner most accommodating to them, to assist with rapport, retention, and the identification of medication changes or adverse events in real-time.

- Interim assessments (week 8/days 56, 57 and week 12/days 84, 85)
 - i. ePROs (days 56 and 84 +/- 1 day) – to be completed in the on-state
 - PDQ-39
 - MDS-UPDRS Part II
 - Transition Questionnaire (day 56 only)
 - ii. Treatment Virtual visits 1 and 2 (days 57 and 85 +/- 3 days)
 - Concomitant medication and adverse event review
 - MDS-NMS (does not include the NMF subscale)
 - Modified MDS-UPDRS Part III (excluding items related to rigidity and postural reflexes)

Virtual visits will be performed using the site's standard of care telemedicine platform.
- End of treatment visit (week 16/days 112, 113 or early termination)
 - i. ePROs (day 112 +/- 1 day) – to be completed in the on-state
 - PDQ-39

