7.8.4.1. Combined measure of MDS-UPDRS Parts I, II, and III (sum score)

This endpoint will evaluate the change in the combined measure of MDS-UPDRS Parts I, II and III. The combined measure of MDS-UPDRS Parts I, II, III will be calculated, inclusive of imputation, as described in SAP v6.0 for RCT Study (Appendix 1). For the passive-active group, the change from corresponding baseline to end of treatment

period will be evaluated using a MMRM model similar to the one described for the primary analysis. Treatment differences will be assessed based on the least-squares mean change scores between the passive and active treatments. Changes meeting or exceeding the previously established MCID for this measure (-6.7 points for clinical improvement)⁸ will be considered clinically meaningful.

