Note: The VISIT effect will be included only when there are multiple post-randomization assessments for a given endpoint. In those cases, a significant interaction between ARM and VISIT will determine a statistically significant finding at a given VISIT. An effect for baseline value will be included for outcomes where the baseline scores significantly different between the treatment arms.

In cases where there is a single post-randomization assessment for a given endpoint, the linear model fit will be simplified to:

$$\begin{split} Y_i &\sim N(0, \sigma^2) \\ Y_i &= \beta_0 + \beta_1 * ARM_i \ + \beta_2 * SITE_i \end{split}$$

where:

 $Y_i = (Endpoint assessment for subject i) - (Endpoint assessment for$

participant i at baseline),

 $ARM_i = 1$ if participant i is in the treatment arm

= 0 if participant i is in the passive arm,

SITE_i is a nominal variable indicating the site for participant i,

The difference between active and passive treatment will be estimated based on the Least Squares Mean (LSMean) difference between the treatment groups from the linear model with the associated confidence interval (CI) and P-value. Additionally, the p-value for the site effect will be presented.

An effect for baseline value will be included for outcomes where the baseline scores significantly different between the treatment arms.

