7.7.2. Secondary Endpoints

Multiplicity of study endpoints will be adjusted for using a hierarchical strategy whereby endpoints in the study are only considered to be statistically significant if both of the following are true: 1) p < 0.05 AND 2) the preceding endpoint was found to be statistically significant at the significance level $\alpha = 0.05$. More specifically, the hierarchical order for evaluation of efficacy endpoints is the following: MDS-NMS Total Score (primary endpoint); the combined measure of MDS-UPDRS Parts I, II and III (secondary endpoint), MDS-UPDRS part II (secondary endpoint); Overall CGI-I (secondary endpoint); MDS-UPDRS part III (secondary endpoint); PDQ-39SI (secondary endpoint). Note that all the secondary endpoints have an *a priori* direction, thus one-tailed tests will be utilized for analyses. Only participants who have baseline data collected for the secondary endpoints will be included in these efficacy analyses.

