7.7.2.1. Combined measure of MDS-UPDRS Parts I, II, and III (sum score)

This endpoint will evaluate the change in the combined measure of MDS-UPDRS Parts I, II and III at the end of the treatment period (day 112 and 113), which is defined based on the change relative to baseline (days 28/29) scores to provide a measure of global function in PD. This outcome will support that TNM[™] Device treatment provide clinically meaningful changes for people with PD. Changes meeting or exceeding the previously established MCID for this measure (-6.7 points for clinical improvement) (Makkos, Kovacs et al. 2018) will be considered clinically meaningful. MDS-UPDRS Part II.

This endpoint will evaluate the change in MDS-UPDRS part II score at the end of the treatment period (day 112) relative to baseline (mean of day 0 and day 28) scores. Changes will be considered to be clinically meaningful if the mean difference (if normal distribution) or median difference (if non-normal distribution) meets or exceeds the previously established MCID (-3.05 for clinical improvement) (Horvath, Aschermann et al. 2017).

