- 17. The International Parkinson and Movement Disorder Society Unified Parkinson's Disease Rating Scale Part I: Non-Motor Aspects of Experiences of Daily Living (MDS-UPDRS I): This endpoint will evaluate the change in MDS-UPDRS I score at the end of the treatment period (day 113) relative to the baseline (day 29).

Treatment adherence, **TNM**TM Device usability/satisfaction (Device Useability Questionnaire) and itemized answers from UPDRS IV assessment tool will also be reported descriptively. To further explore the effects of treatment on individual NMS, effects of treatment on each of the individual MDS-NMS domains will be evaluated. These domains include the following: (1) Depression, (2) Anxiety, (3) Apathy, (4) Psychosis, (5) Impulse control and related disorders, (6) Cognition, (7) Orthostatic hypotension, (8) Urinary, (9) Sexual, (10) Gastrointestinal, (11) Sleep and wakefulness, (12) Pain, and (13) Other. As this is an exploratory analysis, as opposed to a primary or secondary aim, only subjects that demonstrate burden in the specified domain will be evaluated. In practice, this means that if any subject shows no burden on a given MDS-NMS domain throughout the study, then they will be excluded from this exploratory analysis.

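### For RCT participants with no final assessment, the Part III carry-forward cannot produce the combined MDS-UPDRS I+II+III, so the missing-at-random protection stated in RCT SAP 7.10.2 does not reach that endpoint

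*SAP*

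**What the plan says.** The RCT SAP is Appendix 1 of the SAP file. Its section 7.7.2 places the combined MDS-UPDRS I+II+III second in the fixed testing order, directly after the primary endpoint and ahead of four others. Section 7.7.2.1 defines it at one post-baseline point: "at the end of the treatment period (day 112 and 113), which is defined based on the change relative to baseline (days 28/29) scores".

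Section 7.10.2 expects missing data to be missing at random and relies on MMRM for unbiased estimation. If the day-113 Part III is missing after item-level imputation, it takes the last virtual Part III (day 57 or 85), multiplies it by 132/108, and replaces the day-29 baseline with a prorated day-0 value. It then says: "These imputed values for missing data would be applied to both the composite measure for MDS-UPDRS I, II & III and the MDS-UPDRS III" secondary outcomes.

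For Part I, section 7.10.1 has an item-level rule only: "a single item-level missing value can be imputed with the average of the non-missing values for that Part if no more than 1 missing" value exists. Part II has a similar item-level rule, with up to two missing items.

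On the model, section 7.7 states: "In cases where there is a single post-randomization assessment for a given endpoint, the linear model fit will be simplified to" an equation with arm and site as the only terms. A baseline term is added only if the arms differ significantly at baseline.

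**The concern.** Read together, the two statements in 7.10.2 suggest that a participant who misses the final visit is still represented in the combined score, through the imputed Part III and through MMRM. For someone with no final assessment neither holds. The imputed Part III has no Part I to be added to, and the model for this endpoint uses no interim data.

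The ITT population is all randomised participants and is named for the primary analysis of efficacy (RCT SAP 7.2). If non-completers respond less than completers, an analysis of observed scores overstates the effect in that population. The report would meanwhile describe the endpoint as imputed and protected under missing at random. Four later endpoints can be declared significant only if this one is.

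**Working it through.** **1. The plan's own figure.** The documents give no power or SD for the combined score. Their Part I calculation (RCT SAP section 4: 83 per arm, difference 2.64, SD 5.32, two-sided 0.05) reproduces:

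2.64 / (5.32 × √(2/83)) − 1.96 = 3.197 − 1.960 = 1.237, and Φ(1.237) = 0.892, against the stated 89.2%.

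The 83 per arm are already completers: 184 × 0.90 = 165.6, taken as 166.

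**2. Which parts exist when.** From Protocol 4.1.1 and the schedules of events in the Protocol appendix and in the RCT SAP appendix:

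| Time point | Part I | Part II | Part III |
|---|---|---|---|
| Day 0 | no | yes | modified (virtual) |
| Days 28/29 | yes | yes | yes |
| Days 56/57 | no | yes | modified (virtual) |
| Days 84/85 | no | yes | modified (virtual) |
| Days 112/113 | yes | yes | yes |

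Part I is also taken at screening, for eligibility.

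**3. A participant with no final assessment.**
- Part III: supplied by 7.10.2 if a day-57 or day-85 score exists.
- Part II: days 56 and 84 may be on file, but no rule carries them to day 112.
- Part I: no post-randomisation value. The item-level rule cannot replace a whole Part.
- Sum: undefined, so the participant leaves the model.

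**4. What the model then assumes.** A linear model on observed scores with arm and site is unbiased if missingness depends only on arm and site. It is not protected if missingness depends on interim scores, which is the case MMRM handles for endpoints with repeated visits.

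**5. A second gap.** When Part III switches to a day-0 baseline, Part I has no day-0 value and the combined baseline is defined at days 28/29. The SAP does not say whether the baseline sum then mixes a prorated day-0 Part III with day-28/29 Parts I and II.

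**6. How many.** 184 × 0.10 = 18.4, so at most about 18 participants at the planned attrition.

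**7. Illustrative size.** Let completers gain 6.7 points over passive (the MCID in 7.7.2.1), let a fraction m be missing equally in both arms, and let the missing gain e. The effect over all randomised is (1 − m) × 6.7 + m × e.

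| m | e | All randomised | Completer excess |
|---|---|---|---|
| 10% | 0 | 6.03 | 0.67 (0.67/6.03 = 11%) |
| 10% | 3.35 | 6.365 | 0.335 |
| 5% | 0 | 6.365 | 0.335 |

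Both m and e are assumptions; the documents give neither for this endpoint.

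**8. Power.** With all 92 per arm contributing, the Part I calculation gives 92.0% in place of 89.2%. Since the plan counted on completers only, the gap takes nothing from planned power.

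**The case against.** Section 7.10.2 does not promise to impute Part I or to complete every combined score. It says that the imputed Part III value is used in the sum, and that works whenever Parts I and II are present and Part III is missing or unusable. Examples are an OFF-state examination (excluded under 7.7.2.3) or one with more than seven missing items. A reader might infer that the rule is unworkable and that the whole endpoint becomes a complete-case analysis. The documents do not support that: the endpoint needs observed Parts I and II but can still have Part III imputed.

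The final visit is also protected. Protocol 4.1.1 schedules the end-of-treatment battery, Part I included, at early termination as well. Protocol 7.2.1 asks for every effort to complete the final evaluations, virtually if need be, and 4.1.3 allows virtual collection for Covid-19. RCT SAP 7.3 and 7.7.2.3 say how to prorate a virtual final Part III. Many withdrawals may therefore have Part I. This stands, and it makes 18 a ceiling and not an estimate. One ambiguity remains: 7.8.2 explicitly counts early-withdrawal values for the mini-BESTest, whereas 7.7.2.1 is silent for the combined score.

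RCT SAP 7.10.8 names the combined score for sensitivity analyses. One covers completers only. The other compares active completers with the best passive responders if active attrition is significantly higher. The second is a conservative check, but it is conditional and does not address similar dropout in both arms. Neither uses the interim data of participants without a final assessment.

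Finally, one might infer that the OLE has the same defect, because OLE SAP 7.8.4.1 says the score "will be calculated, inclusive of imputation, as described in SAP v6.0 for RCT Study". Part I is likewise absent from the OLE interim visits, but the OLE analysis is a within-person MMRM (OLE SAP 7.8) in which a participant's passive-period value can still contribute. The RCT argument does not transfer without being worked through there.

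**Conclusion.** The concern holds for RCT participants with no final assessment of any kind. They cannot be given a combined MDS-UPDRS I+II+III score under the plan, they leave the arm-plus-site model, and the MMRM statement in 7.10.2 does not cover this endpoint. The number is at most about 18 of 184 at the planned 10% attrition, and unknown below that.

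The 0.67-point (11%) excess should not be read as an estimate of bias. It requires all 10% to be missing with zero benefit, and imputation under missing at random would remove it only as far as baseline and interim scores reveal the poorer response. The matter is the population to which the estimate applies and its possible bias, not power. It should be settled before unblinding, because the endpoint controls whether four others can be claimed.

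**What to change.** In RCT SAP 7.10.2, state that the Part III carry-forward completes the combined score only when Parts I and II are available, and that the MMRM statement applies only to endpoints with repeated post-randomisation visits.

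Then specify:
- Multiple imputation, within arm, of the missing day-112/113 combined score or its parts. Predictors: baseline Parts I to III, Part II at days 56 and 84, and modified Part III and MDS-NMS at days 57 and 85, where available. RCT SAP section 4 cites correlations of 0.75 to 0.85 between MDS-NMS and Part I. Fit the planned arm-plus-site model to each completed data set.
- Whether early-termination and virtual final values count as the day-112/113 score.
- Which baseline the combined score uses when Part III switches to day 0.
- A missing-not-at-random sensitivity analysis, for example imputing a range of poorer outcomes in non-completers.

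For the OLE, check whether the same gap arises under its within-person MMRM, and amend OLE SAP 7.8.4.1 only if it does.

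The cost is SAP text and modest programming on data already scheduled; no visits or participants are added. The drawback is reliance on an imputation model, which has little to draw on for anyone who leaves before day 56.

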7.10.3. Protocol Deviations

To demonstrate the robustness of confounding protocol deviations or violations that impact the interpretation of efficacy analyses, subgroup analyses will be performed utilizing the absence/presence of a confounding deviation to the that element of the protocol (i.e., a change in medication that mimics symptoms of Parkinson's disease occurred, a change in medication used to treat motor and/or non-motor symptoms of Parkinson's disease occurred and/or data was collected at a visit performed out of window when the participant was not treating when protocol requires). Subgroup analyses will be conducted for the primary outcome, the combined measure of the MDS-UPDRS Parts I, II, and III and Mini-BESTest at minimum.

7.10.4. Study blind

Although unlikely, it is possible that knowledge of the study Sponsor and Device name may have the potential to unblind participants or bias them with regard to their expectation of treatment effect. Therefore, the study Sponsor excluded this information from informed consent documents. However, a subset of local institutional review boards and ethics committees required that the Sponsor name be included in the informed consent forms given to the participants at their site. To determine if having the name of the Sponsor in

the informed consent alters the effect of the device, the same modeling methodology used for the efficacy analysis described above will be utilized to determine the effect of having knowledge of the Sponsor name on efficacy, specifically, MMRM will be utilized separately for participants treated at sites where the Sponsor name was included in the ICF vs not included in the ICF. The results of this analysis will be used to determine if knowledge of the Sponsor name affects the relationship between treatment (active or passive) and each outcome. This analysis will be conducted for primary and secondary outcomes.

7.10.5. Comparison to baseline 2

For the primary outcome (at minimum), a confirmatory sensitivity analysis will be conducted to evaluate change in the primary outcome relative to scores obtained during the second baseline assessment only.

7.10.6. Physical limitations

The mini-BESTest (a safety outcome) provides a measure of balance, functional mobility and gait. However, certain aspects of the scale may be negatively impacted due to temporary physical limitations (e.g., lower leg injury) and would be negatively impacted if data was collected in the off-state. Therefore, a confirmatory sensitivity analysis may be conducted that excludes data from study participants that either could not complete all elements of the scale due to bodily injury or impairment (as identified by the scale's rater or ongoing adverse events) or whose data was collected in an off state.

7.10.7. Country and Other Subgroups

An analysis of the primary endpoint and select secondary endpoints will be conducted by country to determine if there is a different treatment effect in the United Kingdom as compared to the United States. For this analysis, separate models will be constructed per subgroup.

Other primary endpoint and select secondary endpoint subgroups to be evaluated include: Sponsor name utilized in ICF (Sponsor name in ICF vs Sponsor not in ICF), Prohibited Concomitant Medication Use (Used vs Not Used), the subset of confounding protocol deviations as noted in section 7.10.3, specifically, a change in medication that mimics symptoms of Parkinson's disease occurred, a change in medication used to treat motor and/or non-motor symptoms of Parkinson's disease occurred and/or data was collected at a visit performed out of window when the participant was not treating when protocol requires (Present, Not Present).

7.10.8. Other

Nonparametric tests that are not impacted by reasons for missing data will also be applied. In this case, only those that completed the study will be evaluated. If attrition in the active treatment arm significantly exceeds that of the passive treatment arm, treatment effects will be evaluated by comparing the active treatment study completers to the best responders of the passive treatment (of equal percentage). These sensitivity analyses will be used to give

greater confidence in the primary outcome and the combined measure of MDS-UPDRS Parts I, II, and III score.

